The Swedish cohort will comprise patients included in the Prescribed Drug Register, who have been prescribed GLP-1 agonists or other anti-diabetic drugs. By linkage to the regional cancer registries in Sweden as well as hospital discharge registries, information on cancer incidence and pancreatitis will be obtained.

Sweden has a highly efficient National Population and Death Register where record linkage has been done effectively on such studies. This gives coverage of all deaths in Sweden and the ability for record linkage ensures that all members of the cohort who die can be identified. In addition, Sweden has a number of other national registers that may be used to add information on potentially confounding factors.

Overall

The personal identification number will be used to link unambigously the databases in each country. The ATC coding system (Anatomic Therapeutic Coding) will be used to identify exposure: all patients having been prescribed drugs for the treatment of diabetes (ATC code A10 and subcategories) will be retrieved and linked to the other databases: they will be followed via cancer and hospital discharge registries. The ICD10 codes will be used for outcome assessment: acute pancreatitis (K85), pancreatic cancer (C25) and thyroid cancer (C73), especially medullary thyroid cancer (Thyroid cancer is a distinct entity in the ICD10 and the tumour type can be determined by the ICD-0 code).

II.9.5 Study size (Sample size and study power)

A key consideration in designing studies is the requirement for a large enough number of events (pancreatitis, pancreatic cancer and thyroid cancer) to provide adequate statistical power to detect an effect. A conservative approach to estimating statistical power has been adopted, since the cumulative rate of events will be greatly increased as longer follow-up time is available.

Assuming an average prevalence of T2DM of 5% (Carstensen et al, 2008) for a total adult population (20+ years) in the 3 countries (Denmark, Norway and Sweden) of 15,000,000, our study population will reach approximately 750,000 subjects.

In terms of exposure to GLP-1 RAs the literature search resulted into a very heterogeneous range of values. An estimation in the THIN database (based on records from a sample of UK GPs) up to the end of 2010 revealed that about 2% of type 2 diabetes patients were treated by GLP-1 agonists. This is likely to be underestimated, knowing that the UK system is usually slower in adopting new drugs. Several cohort studies in the US gave different estimations of exposure to GLP-1 RA: 17% (Garg et al, 2010) 11% (Doré et al, 2009), 2.6% (Romley et al, 2012), that may overestimate use in

Europe because adoption of new drugs is faster in the USA. Since liraglutide is manufactured and marketed by a Danish pharmaceutical company (Novo Nordisk), the proportion of type 2 diabetes patients treated with liraglutide in the Nordic countries is likely to be higher than that observed in the THIN database. We have therefore assumed that a proportion of 5 to 10% of the diabetic patients are exposed to GLP-1 RAs and the following sample size/power calculations are done for these 2 hypothetical values. Conservatively assuming an average follow up of one year for these patients and 5% of diabetics exposed to GLP-1, then 37,000 person-years (p-y) of total follow-up time will be eligible for this study by the end of 2011. Idem, if 10% of diabetics are exposed to GLP-1, then 74,000 person-years (p-y) of total follow-up time will be eligible for this study by the end of 2011.

The incidence rate of acute pancreatitis was estimated using age-specific data from Sandzen et al. (2009) for the period 1998-2003 among the Swedish population, weighted by the age distribution among the diabetic population (Diabetes in the UK April 2012 available at: http://www.diabetes.org.uk/Documents/Reports/Diabetes-in-the-UK-2012.pdf, Carstensen et al., 2008). Age specific incidence rate for pancreatic and thyroid cancer were derived from NORDCAN (www.dep.iarc.fr/nordcan.htm) and also weighted by the age distribution among the diabetic population. The estimated diabetes-age adjusted incidence rates are shown in Table **II.9.5.**1:

Table II.9.5.1: Projected age adjusted incidence rate

Outcome	Diabetes age adjusted incidence rate (per 100,000)
Pancreatitis	65.57
Pancreatic cancer	29.19
Thyroid cancer	6.13

Under these assumptions, the minimal detectable risks (with 90% power and 95% confidence level, model: Poisson distribution) are shown in Table II.9.5.2 (sample size calculations using the methodology of Gu et al. 2008):

Table II.9.5. 2: Minimum detectable risk for one year of follow-up

Exposure to GLP-			
1 among	Acute	Pancreatic	
diabetics	Pancreatitis	cancer	Thyroid cancer
5%	1.80	2.40	5.63
10%	1.54	1.89	3.67

The database study will be completed in 2014. Figure II.9.5.2 shows the evolution of the minimum detectable risk with increasing years of follow-up, for 5% and 10% of exposure to GLP-1 among the diabetic population:

The estimation of sample size and study power for the primary and secondary objectives will be further defined after consultation with local Principal Investigators and external experts.

II.9.6 Data Management

In each centre data will be linked between the different data sources (population registry, prescription registry, hospital discharge registry, cancer registry) through an anonymized unique identification number. Linking the population registry, the prescription registry and the cancer registry has already been tested and proved to be effective through our previous database study (Boyle et al, 2012). However, linking with the hospital discharge registry requires a procedure preventing introduction of information bias in the study.

All patients identified to have had an anti-diabetic treatment in the prescription database (regardless of the type of medication taken) will be linked to the Hospital Discharge Registry. All discharge information will be retrieved for all the diabetic patients (with an

anti-diabetic prescription) and searched for codes or keywords that indicate a pancreatic related disease focussing on acute pancreatitis and pancreatic cancer.

Each national centre will be responsible for the data storage and data management of the individual-level data, following all national and European directives regarding the well being and rights of each study subject. Each centre has an excellent track record of successfully undertaking similar research respecting all moral and legal requirements.

For data analysis, a two stage process will be adopted because it is not possible to share individual level data. In each country an individual level analysis will be carried out using a common statistical methodology. The anonymous results (statistical model coefficients) will be transferred to the coordinating center IPRI in a secured way (password protected). Pooling of the within study effects in a meta-analysis (Thompson et al, 2010), will then be carried out at I-PRI. This same procedure was used successfully in the earlier study. Notably, no identifiable data will be made available outside the country where the data are obtained.

II.9.7 Statistical Analysis

Full details of the statistical analysis will be determined prior to the end of the period of data collection and discussed and approved by the Biostatistics Advisory Committee. This is in a similar manner to the approach adopted in the *Northern European Database Study of Glargine and Cancer* (Boyle et al, 2013). The philosophical approach to the statistical analysis will be in the spirit of this previous study, whose statistical analysis plan is attached as Appendix III.

1. Incidence rates and 95% confidence intervals (CI) of pancreatitis, pancreatic cancer and thyroid cancer among the patients treated with GLP-1 RAs as well as those patients treated with other anti-diabetic medications will be derived. In addition, fitting a Poisson regression model may be considered.

2. Hazard ratios (95% CIs) of pancreatitis, pancreatic cancer and thyroid cancer associated with the treatment of GLP-1 RAs versus other anti-diabetics will be estimated using time-dependent Cox proportional hazards survival analysis. The potential confounding factors listed above will be adjusted for in the analyses (to be further discussed and refined by external experts).

The two types of analyses above (intent-to-treat analysis and an analysis by censoring the follow up time at the end of treatment of either GLP-1 RAs or other anti-diabetics) will be stratified by age, sex, previous anti-diabetic treatments (such as insulin, metformin etc) and other confounding factors in function of their availability.

3. Profile of GLP-1 users as compared to users of other anti-diabetics, for instance: age, sex, previous prescriptions, further covariates when available.

A major strength of the study will be that the Protocol will be followed to the largest extent possible and, notably, the statistical analyses will be restricted to the study hypotheses which have been declared.

II.9.8 Quality Control

The three countries involved in this study have databases which have all been demonstrated to be of the highest quality and completeness. The three countries chosen also have long-established and high-quality National Cancer Registries and Hospital Discharge Registers with diagnostic information. In addition, each of these countries has a National Mortality Database served by long-standing cause of death schemes. The three countries participated in the *Northern European Database Study of Glargine and Cancer* and have a substantial track-record of undertaking cutting-edge pharmaco-epidemiological studies.

With high-quality data available regarding exposure and the endpoints of interest, the study will be further strengthened by identical analyses being carried out in each centre using a common statistical methodology.

IPRI will ensure the coordination of the project through the **Coordination Office.** The Office will comprise the IPRI Principal Investigators and Senior Staff ([name], [name], [name], [name], [name] and [name]): [name] shall act as the Project Manager, will be available for daily contact with each of the national studies and responsible for developing the study database and preparing it for statistical analysis. In addition, Masters-level appointee(s) will work within the Office, coordinating study materials and correspondence, as needed.

The **Scientific Committee** for the study will comprise two representatives of IPRI ([name], and [name]) and two representatives of each of the national studies: [name] and [name] (in Denmark), [name] and [name] (in Norway), [name] and [name] (in Sweden). This group will be responsible for preparing the operational protocol for the study which shall then be passed to the Scientific Committee for approval. The Scientific Committee will ensure the conduct of the study according to the protocol in each of the participating countries, it will be responsible for the statistical analysis, the interpretation of the results and the preparation of the reports. The ultimate responsibility for the study lies with the Scientific Committee. It will meet regularly throughout the study period.

An independent, external **Scientific Steering Committee** will be appointed to oversee the study and advise on treatment, methodological and biostatistical issues. This group will meet regularly throughout the duration of the study and incorporate a **Biostatistical Advisory Group**, to advise on all aspects of the design and data analysis.

This Group will comprise [name] (University of Perugia, Italy), [name] (McMaster University, Hamilton, Canada), [name] (Mount Sinai, New York, United States of America), [name] [name] (University College London, UK); [name] (Robertson Centre for Biostatistics, University of Glasgow, UK) and [name] (Department of Biostatistics, Yale University, USA).

II.9.9 Limitations of research methods

Administrative databases such as those employed in this study suffer from several key limitations including that the reason why a particular treatment was chosen is unknown and the reasons why therapy changed is also unknown. This contributes to the situation of confounding by indication, which can be a major source of concern in such studies leaving findings and conclusions open to a certain level of uncertainty. The Investigators are experienced epidemiologists who have worked extensively with such databases and can maximise the information which can be extracted from such material without overinterpreting what is possible.

Adjustment for confounding will not be available for the entire cohorts established but will only be available for a proportion of patients in the cohort.

II.10 Protection of Human Subjects

Each national centre will be responsible for following all national and European directives regarding the well-being and rights of each study subject. Each centre has an excellent track record of successfully undertaking similar research respecting all moral and legal requirements. At the central office (iPRI, Lyon) no identifiable data will be received from the individual centres.

All approvals necessary to undertake this study will be obtained in each country. In addition, the study protocol and the national approvals will be submitted to the IPRI Ethics Committee who will give tertiary ethical approval.

II.11 Management and Reporting of Adverse events/ reactions

Reporting of adverse events or adverse reactions on individual patients is not appropriate to this form of study where there is no contact between the investigators and the patients.

II.12 Plans for disseminating and communicating study results

At the end of the study, a full Report will be prepared and the MAH will submit this to the CHMP of the EMA. Once the comments of the Rapporteurs have been received, any modifications necessary will be made to the Report which will then be finalised. A manuscript presenting the results of the study will be prepared for publication in a peerreviewed scientific journal and the findings presented at major scientific meetings of relevance to the subject matter e.g. at the Annual meeting of the European Association for the Study of Diabetes (EASD), at the Annual Meeting of the American Diabetes Association (ADA) and the Annual meeting of the American Society for Clinical Oncology (ASCO).

II.13 References cited in the text

Alves C, Batel-Marques F and Macedo AF. A meta-analysis of serious adverse events reported with exenatide and liraglutide: Acute pancreatitis and cancer. Diabetes Res Clin Pract. 2012 Sep 22. pii: S0168-8227(12)00312-9. doi: 10.1016/j.diabres.2012.09.008. [Epub ahead of print]

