Study Size Under conservative assumptions, approximately 37,000 GLP-1 RA treated patients will be eligible for this study by the end of 2011. Assuming an incidence rate of 65.6 per 100,000 p-y for acute pancreatitis, the study will be able to detect (at 5% significance level and 80% power) a minimum risk of 1.53. For an incidence rate of 29.19 per 100,000 p-y for pancreatic cancer and 6.13 for thyroid cancer, the study will

be able to detect a minimum risk of 1.96 for pancreatic cancer and 3.40 for thyroid cancer respectively.

Milestones Key milestones include that data collection will be concluded by mid-2014 and the report will be submitted to the CHMP in December 2014. After receiving the comments of the Rapporteurs, the Report will be finalized in the first quarter of 2015 and an article for a peer-reviewed submitted shortly thereafter.

II.5 Amendments and Updates

This is the initial protocol and any amendments will be placed here in a timely manner.

II.6 Milestones (events in months)

- T0 Study preparation starts
- T3 Protocol agreed and submitted to CHMP EMA
- T6 Development of data collection module
- T6 Final agreement on Protocol from CHMP
- T8 Preliminary Pilot Testing of data collection and data transfer
- T9 IRB/Ethics Approval as required at each site.
- T10 Data collection begins in each country
- T12 Interim report submitted to CHMP/EMA
- T18 Data Collection complete
- T21 Data Cleaning and Data Analysis.
- T24 Submission of Report to CHMP/EMA
- T26 Comments received from Rapporteurs
- T27 Finalization of Report
- T28 Submission of Article to peer-reviewed journal

II.7 Rationale and Background

Glucagon-like peptide 1 receptor agonist (GLP-1 RA) is a new class of blood glucose lowering drugs indicated in the treatment of type 2 diabetes mellitus (T2DM). It is an agonist molecule to the incretin (gastrointestinal hormone) GLP-1 which stimulates glucose-dependant secretion of insulin. GLP-1 is rapidly inactivated by the dipeptdyl peptidase-1 (DPP-4) (half-life of about 2 minutes), hence the need for a GLP analogue or agonist with greater resistance to DDP-4 degradation. GLP-1 regulates glucose levels by stimulating glucose-dependent insulin secretion and biosynthesis, and by suppressing glucagon secretion, delayed gastric emptying and promoting satiety.

There are currently 2 GLP-1 RA products on the market, one of which (exenatide) is available in two formulations (Byetta and Bydureon):

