Using these hypothetical numbers, the number of patient-years accumulated over a period of 5 years of registry were calculated as follows:

1st year of registry: no records yr1 = %lixi * prevalence diabetes = %lixi * 1,049,810 2nd year of registry: no records yr2 = no records yr1 + new records yr2= no_records_yr1 + %lixi * new_cases_diabetes = no_records_yr1 + %lixi * 55,000 3rd year of registry: no_records_yr3 = no_records_yr2 + new_records_yr3 = no_records_yr1 + 2 * %lixi * new_cases_diabetes

etc...

Thus the number of person-years accumulated over 5 years is: Person-years_over_5_years = no_records_yr1 + no_records_yr2+..+ no_records_yr5 =5*(%lixi*prevalence_diabetes)+10*(%lixi*new_cases_diabetes)

The number of expected cases of pancreatitis were calculated using the incidence rate shown above (65.57 per 100,000 person-years). The power of the study was then calculated for the expected number of cases as a mean of Poisson law (Breslow and Day, 1987) and a range of expected vs observed ratios. The results are shown in Table III.9.5.1.

Table III.9.5.1: Estimates of statistical power for Registry Study for pancreatitis under different scenarios for prevalence of prescription of lixisenatide.

Pancreatitis (incidence rate=65.57/100,000 pyrs)						
	Pyrs No of Power in order Power in order Power in o					
% exposure to	accumulated	expected	to detect	to detect	to detect	
lixisenatide	over 5 years	cases	obs/exp+=1.2	obs/exp+=1.5	obs/exp+=2	
0.10%	5799.05	3.8	0.10*	0.17	0.39	
0.20%	11598.1	7.6	0.13*	0.26	0.64	
0.50%	28995.25	19.0	0.18	0.60	0.97	
0.80%	46392.4	30.4	0.27	0.79	1.00	
1.00%	57990.5	38.0	0.29	0.83	1.00	
1.50%	86985.75	57.0	0.37	0.93	1.00	
2%	115981	76.0	0.47	0.98	1.00	
5%	289952.5	190.1	0.38*	1.00	1.00	
10%	579905	380.2	0.60*	1.00	1.00	
*Calculated using normal approximation						
tobs /exp stands for 'observed us expected ratio'						

+obs/exp stands for 'observed vs expected ratio

These numbers are certainly underestimated, as the incidence of diabetes has been steadily increasing worldwide. Even so, for a 1% exposure to lixisenatide among diabetic patients, thus 38 expected cases of pancreatitis, the power of the study in order to

detect an observed vs expected ratio of pancreatitis of 1.5 will be of 83% (significance level=0.05).

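### The synopsis detectable risks for the database study (1.53 / 1.96 / 3.40 at 80% power) do not follow from the power calculation in II.9.5 and should be reconciled with it

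*Protocol*

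**What the plan says.** The Study Size paragraph of the database study synopsis assumes that "approximately 37,000 GLP-1 RA treated patients will be eligible for this study by the end of 2011". At an acute pancreatitis rate of 65.6 per 100,000 person-years it states that "the study will be able to detect (at 5% significance level and 80% power) a minimum risk of 1.53". It continues "For an incidence rate of 29.19 per 100,000 p-y for pancreatic cancer and 6.13 for thyroid cancer", and says the study will "be able to detect a minimum risk of 1.96 for pancreatic cancer and 3.40 for thyroid cancer respectively". It names no test and does not say whether the 5% level is one- or two-sided.

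Section II.9.5 starts from a diabetic population in which "our study population will reach approximately 750,000 subjects". It takes 5% or 10% as exposed and one year of average follow-up, which gives 37,000 or 74,000 exposed person-years, and uses the same three rates (Table II.9.5.1). Table II.9.5.2 then gives detectable risks "with 90% power and 95% confidence level, model: Poisson distribution": 1.80 / 2.40 / 5.63 at 5% exposure and 1.54 / 1.89 / 3.67 at 10%, in the order acute pancreatitis, pancreatic cancer, thyroid cancer. The cited method is a paper on tests for the ratio of two Poisson rates. Sidedness is not stated here either, and 80% power does not appear in II.9.5.

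Section II.9.7 plans to report "Hazard ratios (95% CIs) of pancreatitis, pancreatic cancer and thyroid cancer associated with the treatment of GLP-1 RAs" versus other anti-diabetics. The hypotheses in II.8 are all worded as an increased risk.

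**The concern.** The synopsis should summarise II.9.5, yet for the same exposed group and rates it gives a different set of ratios at a different power. Some reduction is expected on going from 90% to 80% power. The question is whether that change accounts for the whole difference. If it does not, the synopsis credits the study with a sensitivity that its own power section does not support. For a post-authorisation safety study reported to the CHMP, the stated detectable risk guides how much reassurance a finding of no increase can give.

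**Working it through.** **Inputs.** Rates λ are 65.57, 29.19 and 6.13 per 100,000 person-years (Table II.9.5.1; III.9.5 repeats the first as "calculated using the incidence rate shown above (65.57 per 100,000 person-years"). Total person-years are 750,000, from 750,000 subjects followed for one year on average. At 5% exposure t1 = 37,000 and t0 = 750,000 − 37,000 = 713,000. At 10% exposure t1 = 74,000 and t0 = 676,000. Expected exposed cases at a ratio of 1 in the 5% scenario are λ × 37,000 = 24.26, 10.80 and 2.27.

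**Formula.** For the unconstrained Wald test of two Poisson rates, with rate ratio R:

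power = Φ( (R − 1)λ / √(Rλ/t1 + λ/t0) − z ), with z = 1.645 for one-sided 5% and z = 1.960 for two-sided 5%.

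**Step 1: reproduce Table II.9.5.2.** Solve for R at 90% power.

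| Exposure | Printed | One-sided 5% | Two-sided 5% |
|---|---|---|---|
| 5% | 1.80 / 2.40 / 5.63 | 1.81 / 2.39 / 5.63 | 1.93 / 2.61 / 6.52 |
| 10% | 1.54 / 1.89 / 3.67 | 1.54 / 1.89 / 3.67 | 1.61 / 2.02 / 4.14 |

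The one-sided version matches all six cells within about 0.01. No other variant tried fits all six. At two-sided 5% the printed ratios have about 83% power by this formula.

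**Step 2: change only the power, to 80%.** With 37,000 exposed person-years and one-sided 5%, the formula gives 1.66 / 2.11 / 4.54, against 1.53 / 1.96 / 3.40 in the synopsis. Two-sided it gives 1.77 / 2.31 / 5.31.

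**Step 3: power at the synopsis ratios, same formula, one-sided.** Multiplying numerator and denominator by t1 puts both in units of exposed cases. The numerator becomes (R − 1)λt1 and the standard error √(Rλt1 + (t1/t0)λt1), with t1/t0 = 0.0519.

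| Outcome | R | (R − 1)λt1 | Standard error | Ratio − 1.645 | Power |
|---|---|---|---|---|---|
| Acute pancreatitis | 1.53 | 12.86 | √(37.12 + 1.26) = 6.20 | 0.43 | 67% |
| Pancreatic cancer | 1.96 | 10.37 | √(21.17 + 0.56) = 4.66 | 0.58 | 72% |
| Thyroid cancer | 3.40 | 5.44 | √(7.71 + 0.12) = 2.80 | 0.30 | 62% |

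Two-sided, the corresponding powers are 55%, 60% and 49%.

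**Step 4: look for another test that gives the synopsis triple.** One-sided 5%, 80% power, 37,000 v 713,000 person-years unless noted:

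| Test | Detectable ratios |
|---|---|
| Synopsis | 1.53 / 1.96 / 3.40 |
| Wald, as in Step 1 | 1.66 / 2.11 / 4.54 |
| Square-root | 1.59 / 1.93 / 3.41 |
| Score (constrained variance) | 1.56 / 1.88 / 3.18 |
| Log rate ratio | 1.53 / 1.80 / 2.85 |
| Exact one-sample Poisson, 37,500 person-years (5% of 750,000) | 1.58 / 1.96 / 3.44 |

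Each synopsis value appears or is approached somewhere, but no row gives all three. The log test that returns 1.53 gives 1.80 and 2.85 for the cancers. Two-sided versions, 90% power, a 1:1 comparator and a scan of exposed person-years from 15,000 to 150,000 did not produce the triple either.

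**The case against.** The synopsis names no method, so imposing the Wald statistic on it is a choice. Under the square-root test the synopsis ratios have about 74%, 82% and 80% power; under the log test, about 80%, 90% and 93%. The exact one-sample test at 37,500 person-years comes within about 3% of every synopsis figure. This part stands. A reader might infer that all three synopsis values are too favourable by a known amount, worst for thyroid cancer. The documents do not support that: with about 2.3 expected exposed thyroid cancers the normal approximations differ widely, and 3.40 is close to several one-sided 80% results. Setting 3.40 directly against 5.63 also mixes two power levels.

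A reader might also infer that Table II.9.5.2 itself overstates detectability because it is one-sided. That is not shown. One-sidedness is inferred from the match and not stated, two of the six cells agree only to 0.01, and the cited method paper is not at hand. A one-sided planning test is compatible with hypotheses of increased risk. Nor does a two-sided test always give larger ratios than the table: an exact conditional two-sided test at 90% gives 1.80 / 2.30 / 4.58 at 5% exposure.

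Finally, the figures set no enrolment target. One year of follow-up is described as conservative, observation runs beyond 2011 (II.9.3), and II.9.5 says that power will be defined further. This limits the consequence. It does not reconcile two sets of figures built on the same 37,000 and the same rates.

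**Conclusion.** The synopsis figures contradict the protocol's own power section, and the change from 90% to 80% power does not account for the difference. By the calculation that matches Table II.9.5.2, the 80% values are about 1.66 / 2.11 / 4.54, and the synopsis ratios carry about 67%, 72% and 62% power. As a set, 1.53 / 1.96 / 3.40 comes from none of the tests tried. The figure of 1.53 has the least support: only the log test reaches it, and that test does not give the other two. The size of the overstatement for the two cancers depends on the test and is not settled by the documents.

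The numbers rest on 37,000 v 713,000 person-years, the Table II.9.5.1 rates, and the inference that the table is a one-sided Wald calculation. That the two places disagree does not depend on this inference. On sidedness the finding is limited to an undeclared choice: an apparently one-sided table beside 95% intervals that are conventionally two-sided.

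**What to change.** Use one set of figures in the synopsis and in II.9.5. Either quote the 5% exposure row of Table II.9.5.2 in the synopsis with its 90% power, or recompute the synopsis at 80% by the II.9.5 method. The latter gives about 1.66 / 2.11 / 4.54 if the sponsor confirms the one-sided Wald calculation; if another method was used, name it and recompute from that.

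In both places, name the test and say whether the 5% level is one- or two-sided. If one-sided, justify it by the directional hypotheses and note that it does not correspond to the 95% intervals in II.9.7. If the planning is meant to match those intervals, the same method two-sided at 90% gives about 1.93 / 2.61 / 6.52 at 5% exposure and 1.61 / 2.02 / 4.14 at 10%.

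The cost is a text correction. Design, data collection and analysis are unchanged; with the Wald method the synopsis figures become less favourable.
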